**6. SPECIFIC AIMS**

Primary Aim: In healthy, cognitively intact elderly subjects, determine the effects of an 8-week synbiotic supplement intervention on the stool microbiome (pre- and post-intervention) as compared to *Triphala* alone and placebo.

Secondary Aim: In healthy elderly subjects, examine the effects of an 8-week synbiotic supplementation intervention on inflammatory blood markers compared to herb alone or placebo.

Exploratory Aim 1: In healthy elderly subjects, examine the effects of an 8-week synbiotic intervention on gastrointestinal and psychological health via questionnaires compared to herb alone or placebo.

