
Our overarching research goal is to help reduce early morbidity from aging and mortality associated with infection in the aged by developing probiotics with the potential to enhance the health benefits of *Triphala* to reverse chronic inflammation and stimulate immune robustness. Our project is based on the hypothesis as well as *in vitro* data from our laboratory which demonstrate that the bioactivity of *Triphala* is elicited by the gut microbiome to generate a widened spectrum and abundance of anti-inflammatory compounds. We reason that the *Triphala*-induced benefits to both the elderly as well as persons of all ages can be enhanced by co-administration of specific probiotic species. *Thus, we hypothesize that probiotic formulations consisting of bacterial species capable of mediating the increased digestion, bioabsorption and bioactivity of Triphala will increase and make more uniform the response and impact of Triphala treatment on human populations. We hypothesize that the potent anti-inflammatory Triphala when co-administered with VSL#3 will further reduce inflammation and promote a healthier gut community architecture in the elderly.*

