## **Assessment Outcomes**

Outcomes Hypothesis: Feasibility, treatment expectancy/satisfaction, retention, and adherence.

Recruitment rates will be recorded and new recruitment strategies will be formulated to overcome barriers presented by decliners for a future study. Treatment expectancy and satisfaction - 6 item credibility/expectancy questionnaire (CEQ) will be utilized. Retention (% of drop-outs) will be recorded, and exit interviews will be administered to determine reasons for drop-out. Adherence to intervention will be derived from T1 and T2 presence.

Outcomes Hypothesis: Objective measures of gut microbiome health.

*16S rDNA Sequencing:* Stool samples will be analyzed to identify alterations in the gut microbiota community structure by 16S rDNA sequencing. This experimental design will allow us to assess the efficacy of *Triphala* and probiotic species to positively modulate inflammaging and immunosenescence. We will also assess a panel of 30 cytokine/chemokines/lymphokines for this purpose. Finally, our study design permits us to evaluate potential synergistic interactions between the probiotic species and *Triphala*.

Outcomes Hypothesis: Objective measures of inflammatory status.

*Blood pressure (BP):* 3 resting automated BPs will be taken (Dinamap 1846SX) and averaged.

*Biomarkers:* Blood samples will be obtained by a licensed phlebotomist from a mobile phlebotomy service, Veni-Express in SOM Building 4's Clinical Rooms. Serum heparin or EDTA-preserved plasma will be stored at -80° C until assay in [name] laboratory space MTF-418. Inflammatory biomarkers will be assessed by ELISA (MSD, Minneapolis, MN).

For those participants who specifically consent to tissue banking in the ICF, their samples will remain in storage in [name] laboratory space MTF-418 after the end of this study. These blood and stool samples will remain under the sole control of the PI and may be investigated later for other inflammation-related biomarkers and gut microbes.

Exploratory Outcomes Hypothesis: Health-related behaviors.

*Pittsburgh Sleep Quality Index (PSQI):* A self-report of sleep quality and disturbances over a 1-month period.

Nineteen items generate seven "component" scores. The sum of scores yields one global score;

*Fruit/Vegetable/Fiber Screen and Fat Screen:* Rapid screeners with high correlations for total fat, saturated fat, cholesterol, fruit/vegetable intake.

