#### **Statistical Issues**

Analytic Approach. Summary statistics (means, SDs, ranges, frequencies) will be computed for all variables of interest and compared between the treatment arms at baseline using 2-sample tests to test if randomization achieved balance in key covariates across groups. In the event of pre-existing variable group differences associated with dependent or relevant clinical variables, the nuisance variables will be statistically controlled. Outcome measures (e.g. health-related behaviors, psychological health, and objective measures of microbiome health and inflammation) will be transformed as needed to better approximate Gaussian distributions. The proposed study period is 2 months; hence we anticipate little loss-to-follow-up. However, subjects may drop out for a variety of reasons. It is important to take missing data into account when testing hypotheses of interest. Mixed-models can be applied even if some observations are missing as long as the data are "missing at random". Missing data (e.g., drop-outs) will be tested to determine if it is informative, and the methods to test for completely random dropouts will be applied. If needed, pattern-mixture models will be developed which take "missingness" into account when estimating parameters of interest using the methods of Park & Lee.

Analysis Plan. Two sample *t*-tests will be used to compare change scores (post-treatment minus pretreatment) in each outcome. Given the multiple outcomes, we will also use O'Brien's test which can be used to compare multiple endpoints across groups; we will apply O'Brien's test to the multiple outcomes for each hypothesis (e.g., psychological health via positive and negative affect, depressive symptoms; health behaviors via diet, physical activity, medication adherence, and alcohol usage). The O'Brien test statistic is a weighted linear combination of the *t*-statistics for each outcome. Finally, we will fit mixed effects models, with a subject-specific intercept included to allow for individual variability in outcome. Main covariate effects will be treatment group, time (pre-treatment and immediately post-treatment), and the group X time interaction. Likelihood ratio tests will be used to test the significance of these covariates. A significant group X time interaction will indicate that outcome trajectories differ across treatment groups.

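### The primary aim concerns gut community structure, but the analysis plan has no community-level or compositional test, and its only joint test, O'Brien's, is nearly blind to shifts in both directions

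*Combined protocol and SAP*

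**What the plan says.** Section 6 (Specific Aims) sets the primary aim: "determine the effects of an 8-week synbiotic supplement intervention on the stool microbiome (pre- and post-intervention"), compared with *Triphala* alone and placebo. It names no metric. Two other places define the target. Assessment Outcomes states: "Stool samples will be analyzed to identify alterations in the gut microbiota community structure by 16S rDNA sequencing". The hypothesis that closes section 7 is that the combination will "promote a healthier gut community architecture in the elderly".

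Statistical Issues gives microbiome measures no method of their own. They appear in one list with health behaviours and psychological scales, and "objective measures of microbiome health and inflammation) will be transformed as needed to better approximate Gaussian distributions". Three analyses follow:

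- two-sample t-tests, which "will be used to compare change scores (post-treatment minus pretreatment) in each outcome";
- a joint test: "we will apply O'Brien's test to the multiple outcomes for each hypothesis", described there as a weighted linear combination of the t-statistics;
- "we will fit mixed effects models, with a subject-specific intercept included to allow for individual variability in outcome", with group, time and their interaction judged by likelihood ratio tests.

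The documents name no diversity index, distance, taxon list, log-ratio transform, multivariate or distance-based test, or false discovery control. The section reads as complete, so this is not an effect of redaction.

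**The concern.** Community structure is multivariate: some taxa rise while others fall. A plan built for questionnaire scores raises two problems.

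The first is certain. The only analysis that combines outcomes adds up signed t-statistics, so rises and falls cancel. The primary question then has no joint test suited to it.

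The second is conditional. 16S data are shares that sum to one. The synbiotic arm swallows bacteria twice daily, and section 7 expects a bloom of *Bifidobacteria* and *Lactobacillus*. If taxa are analysed one by one as shares, extra reads from those genera lower every other taxon's share with no real change in it. A Gaussian transform such as the log does not remove this.

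The plan says the findings will inform a larger trial. A missed community effect, or a spurious loss of resident bacteria, would carry forward into that design.

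**Working it through.** The documents give no figure for the microbiome analysis, so there is none to reproduce. From the plan come 20 completers per arm, three arms and two-sided alpha 0.05. Read shares, variances and numbers of taxa are assumptions.

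**1. Do the listed methods test community structure?**

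*O'Brien's test.* Shares sum to 1 at T1 and at T2, so each participant's changes in share sum to 0. Centred log-ratio changes also sum to 0. A rise in one taxon must be matched by falls elsewhere, so mixed directions are built into the data. A signed linear combination tends to cancel unless each taxon's expected direction is fixed beforehand, and the plan fixes none.

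Simulation: two arms of 20, 50 independent Gaussian taxa, half of the affected taxa shifted up and half down, 400 replicates, 199 permutations. Percentage of runs rejecting:

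| Shift | O'Brien | Permutation test, Aitchison distance | Per-taxon t, Bonferroni | t on a scalar dispersion summary |
|---|---|---|---|---|
| none | 3.5 | 4.75 | 4.0 | 5.25 |
| 0.5 SD, 50 of 50 taxa | 4.75 | 100 | 85 | 95.25 |
| 0.75 SD, 20 of 50 | 4.25 | 100 | 94.5 | 88.5 |
| 0.75 SD, 50 of 50 | 2.25 | 100 | 100 | 100 |

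*Mixed model.* It is fitted outcome by outcome. With two visits and complete data, its group-by-time term carries essentially the same information as the change-score t-test, so it adds no joint test.

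**2. How large are false decreases if taxa are tested as log shares?**

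Let the dosed genera go from share a to share b in the synbiotic arm. Every unchanged taxon's share is multiplied by (1 − b)/(1 − a), so its log share shifts by δ = ln[(1 − b)/(1 − a)]. Assume 60 unchanged genera and a within-person SD of log abundance of 0.5 per visit.

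- SE of the difference in mean change = 0.5 × √2 × √(2/20) = 0.2236.
- Noncentrality = δ/0.2236 on 38 degrees of freedom, critical value 2.024.
- Expected number flagged = 60 × P(|t| > 2.024). By chance this is 60 × 0.05 = 3.0.

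| a to b | Change in share | δ | Noncentrality | Flagged of 60 | Of which decreases |
|---|---|---|---|---|---|
| 2% to 10% | −8.2% | −0.085 | −0.38 | 4.0 | 3.4 |
| 2% to 20% | −18.4% | −0.203 | −0.91 | 8.6 | 8.5 |
| 2% to 30% | −28.6% | −0.336 | −1.50 | 18.7 | 18.7 |
| 0% to 10% | −10.0% | −0.105 | −0.47 | 4.5 | 4.0 |
| 0% to 20% | −20.0% | −0.223 | −1.00 | 9.8 | 9.7 |
| 0% to 30% | −30.0% | −0.357 | −1.60 | 20.6 | 20.6 |

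Simulations of this set-up agree: about 4 genera at 10%, 9 at 20% and 19 to 21 at 30%. After a centred log-ratio transform the count stays between 2.9 and 3.3.

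A different simulation design (50 taxa, 20,000 reads, one taxon truly raised) gave false decreases per unchanged taxon, nominal 2.5%, of 3.0% for a 3-fold rise in a 2% taxon and 82.9% for a 10-fold rise in a 20% taxon. On the centred log-ratio scale the range was 2.9% to 4.1%.

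**3. Does a standard community test answer the question as it stands?**

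Only if the dosed taxa are handled. With three arms of 20, no resident change and one dosed taxon rising from 2% to 10%, PERMANOVA on centred log-ratio shifts of all taxa rejected in 98% to 99% of runs. On resident taxa alone it rejected in 4% to 6%, close to nominal.

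The log-ratio must also be recomputed after the exclusion. With 60 residents and one dosed taxon, a 2% to 10% rise leaves each resident's centred log-ratio lower by (ln 5 + 0.085)/61 = (1.609 + 0.085)/61 = 0.028. Recomputed on residents only, it is 0.

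**The case against.** The strongest reply is that the plan does not say how the 16S data will be summarised. Its wording about measures of microbiome health fits a scalar such as Shannon diversity or an ordination score, for which a t-test or mixed model is reasonable. Transformation as needed does not exclude a log-ratio. The study is also an exploratory pilot that openly leaves multiplicity uncontrolled.

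Much of this stands, and it limits the point. A reader might infer that the plan cannot test community structure at all. The documents do not support that. In the table above, Bonferroni-adjusted per-taxon t-tests had 85% to 100% power and a scalar t-test 88.5% to 100%. What is missing is a named summary and a suitable joint test.

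A reader might also infer that the synbiotic arm's taxon results will be biased towards losses. That needs taxon-level tests on relative abundances, which the plan nowhere states, and a large bloom, for which it gives no size. From 2% to 10% the excess is about one genus in 60.

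The reply does not rescue the joint test. The plan assigns O'Brien's test to the outcomes of each hypothesis, and that method does not suit this target however exploratory the study is. The transformation clause aims at normality, which a log of shares can meet while leaving the closure effect in place.

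**Conclusion.** The point holds in this form. For its primary aim the plan specifies no microbiome endpoint, no community-level test, no compositional handling and no false discovery control. Because O'Brien's test is a stated choice, this is more than a missing detail. Its power stays near or below the nominal 5% when shifts balance, where a permutation test on log-ratio distance reached 100%. That contrast rests on assumed shifts of 0.5 to 0.75 SD split evenly in direction. O'Brien's test would do better if most taxa moved one way, or if directions were fixed in advance.

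False taxon decreases are a conditional risk: slight for a 2% to 10% rise (about 4 of 60 flagged against 3) and material at 20% to 30% (about 9 to 21). Those counts depend on the assumed read shares, the SD of 0.5 and 60 unchanged genera. This should be changed before the data are analysed.

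**What to change.** In Statistical Issues:

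- Name as the primary microbiome test a three-arm PERMANOVA on each participant's centred log-ratio shift (T2 minus T1, Euclidean distance on that scale, i.e. Aitchison), permuting arm labels across participants.
- Fix in advance the taxonomic level, the prevalence filter and the zero-replacement rule. The centred log-ratio is undefined at zero, and 16S tables contain many zeros.
- Run the primary test on resident taxa, with the VSL#3 genera excluded and the log-ratio recomputed. Section 7 names *Lactobacillus* and *Bifidobacteria*; take the full list from the product specification.
- Report the all-taxa version separately, noting that it can be significant merely because ingested bacteria appear in stool.
- Do not use O'Brien's test for taxa.
- Compare single taxa between arms by centred log-ratio change, with false discovery rate control.
- Keep t-tests or mixed models for named scalar measures such as Shannon diversity.

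The cost is revised wording, a little more analysis work and free software, with no new data. There are two drawbacks. Results will depend somewhat on the zero rule. The primary test will also miss effects on resident members of the excluded genera, which matters because section 7 expects *Triphala* itself to raise both of the genera it names. The all-taxa and single-taxon results for *Triphala* alone against placebo, where no bacteria are ingested, would still show such an effect.

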**Exclusion criteria:**

- 1) Alzheimer's Disease or other neurodegenerative disease such as Parkinson's Disease;
- 2) Current use or use in the past 3 months of antimicrobial or steroid drugs;
- 3) Medical conditions affecting immune status (e.g., heart failure, inflammatory bowel disease, hepatitis C, HIV);
- 4) International travel in the past 3 months.
- 5) Previous known side effect or negative reaction to VSL#3 or *Triphala*.

Note that heart failure, inflammatory bowel disease, hepatitis C, and HIV patients are excluded due to these diseases featuring variable and significantly altered immune status and gut microbiome, which are the main outcome measures of the study. This pilot study seeks to identify relatively healthy elderly subjects to assess these markers in the context of dietary supplementation.

**Assessment visits.** Assessment personnel will be naive to the participant group assignment. Testing will take place at SOM Building 4. At T1 (baseline): participants will 1) review their study responsibilities with the opportunity to reconsider participation 2) provide a stool and small blood sample for biomarker assessment; 3) complete psychosocial measurements via questionnaires; 4) receive group assignment instructions at the end of the visit. Measures will be repeated at T2 (post-intervention period).

**Randomization.** A computer-generated randomization algorithm will determine group assignment to ensure that participant demographics are evenly distributed across study conditions.

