Sample Size and Power. We hypothesized a Cohen's *d* effect-size (standardized mean difference between groups) of 0.75 based on previous studies. With at least 60 subjects completing 2 visits, we will have 80% power (2-sided alpha=0.05) to detect a 0.75 effect-size (Cohen's *d*). To be conservative, we aim to recruit 75 subjects to this study, allowing for a 20% drop-out/loss-to-follow-up rate and a total of 60 subjects completing the 2 visits. Note that our calculations did not control the Type I error for the multiple endpoints. Our objective in this small pilot study is to obtain early evidence of the putative efficacy of this novel intervention on a multitude of outcomes, psychosocial and biological, in the elderly. We expect our findings to inform the design of a larger future clinical trial in elderly subjects.

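### Pattern-mixture modelling is tied to a test for informative drop-out that observed data cannot provide, and it has no stated identifying assumption

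*Combined protocol and SAP*

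**What the plan says.** All of this stands in Section 9, Statistical Issues, unless noted.

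- The Analytic Approach gives the reason for mixed models: "Mixed-models can be applied even if some observations are missing as long as the data are" missing at random.
- It continues: "Missing data (e.g., drop-outs) will be tested to determine if it is informative", and in the same sentence adds that "the methods to test for completely random dropouts will be applied".
- The next step is conditional: "If needed, pattern-mixture models will be developed". The form is left to a published method that is cited by author only and has no entry in the bibliography (Section 22). No test, significance level, decision rule, identifying restriction or sensitivity parameter is given.
- The Analysis Plan lists two-sample t-tests on change scores first, then O'Brien's test, then mixed models with group, time and their interaction. The mixed models are not conditional on any test. None of these is named as the main analysis.
- Outcomes are taken at T1, and "Measures will be repeated at T2 (post-intervention period"). There is no visit in between. Exit interviews record reasons for leaving, and a monthly form records medication changes. Neither supplies a T2 outcome.
- Sample Size and Power recruits 75 to obtain 60 completers, "allowing for a 20% drop-out/loss-to-follow-up rate", although the Analytic Approach expects few losses over two months.

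**The concern.** Drop-out is informative when it depends on the value that was not seen, given what was seen. Here the unseen value is T2. The plan proposes to test for this and, read in order, to let the answer decide whether a pattern-mixture model is built. Two things go wrong.

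First, the data hold nothing that can answer the question. A non-significant result would not show that drop-out is harmless. A significant one would show only that baseline is related to leaving, which is compatible with missing at random.

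Second, if a pattern-mixture model is attempted, the drop-out pattern contains no T2 data. The treatment effect averaged over patterns then depends on an assumption about those values, and the plan leaves it to be chosen after the data are in.

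At stake is whether the pilot reports how far its effect estimates depend on the people who left. Those estimates are meant to inform a larger trial.

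**Working it through.** **Inputs from the documents.** 75 recruited, 60 completers and 20% loss (Sample Size and Power); 3 groups of 20 completers (Section 10); two-sided alpha 0.05 and d = 0.75 (Sample Size and Power); two outcome times.

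**1. The plan's own figure.** 60 / (1 - 0.20) = 75, which reproduces. Expected drop-outs: 75 - 60 = 15, or about 5 per group.

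**2. Power of the test that the data allow.** Compare T1 values of drop-outs and completers with a two-sample t-test. The noncentrality is d × sqrt(n1 × n2 / (n1 + n2)).

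- All arms together, 15 v 60: sqrt(900/75) = 3.464, with 73 degrees of freedom.
- Within one arm, 5 v 20: sqrt(100/25) = 2.0, with 23 degrees of freedom.

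| Baseline difference | Power, 15 v 60 | Power, 5 v 20 |
|---|---|---|
| 0.3 SD | 18% | 9% |
| 0.5 SD | 40% | 16% |
| 0.75 SD | 73% | 30% |

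This is power against a departure from completely random drop-out. It is not power against informative drop-out.

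**3. What that test does when drop-out is informative.** Simulation: 25 per arm, 5 drop-outs per arm, 4,000 runs, no true effect, assumed T1-T2 correlation of 0.3 to 0.7. In one arm the five subjects with the worst T2, after removing the part explained by T1, drop out. In the other arms drop-out is random.

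- The baseline test rejects in 4% to 6% of runs, which is about its nominal level.
- The completer change-score contrast is biased by 0.27 to 0.31 SD, and its type I error is 15% to 20%.

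This case is deliberately extreme. At 20% loss it corresponds to a departure of 0.27/0.20 = 1.35 to 0.31/0.20 = 1.55 SD. It shows that the test can stay silent while bias is present; it does not forecast the size of the bias. When drop-out depends on T2 itself or on the change, the test rejects in 9% to 27% of runs, but only because those quantities are correlated with baseline.

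**4. What a pattern-mixture model can estimate.** With 3 groups × 2 times × 2 patterns there are 12 means. The data inform 9. The other 3 are the drop-outs' T2 means, one per group, and the group-by-time effect averaged over patterns needs them.

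**5. Size of the dependence.** Let p be the fraction lost in one arm, and let delta be the amount by which the unseen mean change of its drop-outs differs from that of its completers. The arm mean, and so the contrast, shifts by p × delta.

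- p = 0.20, delta = 0.5 SD: 0.10 SD.
- p = 0.20, delta = 1.0 SD: 0.20 SD, which is 0.20/0.75 = 27% of the planned effect.
- p = 0.10, delta = 1.0 SD: 0.10 SD.

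The standard error of a 20 v 20 contrast is sqrt(2/20) = 0.316 SD, so shifts of 0.10 and 0.20 are 0.32 and 0.63 standard errors. The values of delta, and the 10% loss in the last line, are assumptions.

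**The case against.** The strongest reply is that the plan already contains a sound analysis for incomplete data. Mixed models are to be fitted whatever any test shows, and they use the T1 values of drop-outs. This stands, and it matters. In a simulation with 25 v 25, five drop-outs per arm and drop-out in one arm driven by baseline, the completer change-score contrast was biased by about 0.1 to 0.24 SD of a single measurement. A likelihood-based estimate using all T1 data had bias of about 0. A reader might infer that the completer t-tests will stand alone; the documents do not support that. But the mixed model rests on missing at random and so cannot check it.

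Other parts of the reply also stand.

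- The test of completely random drop-out is planned and feasible.
- The link from the test to the pattern-mixture model is implied by the order of the sentences and is not a written rule. If it is not a trigger, the analysis is simply discretionary.
- A reader might blame the two-visit design. Informative drop-out cannot be tested from observed data with any number of visits. Two visits matter only because a drop-out then contributes baseline and nothing more.
- A reader might conclude that no pattern-mixture model can be fitted. A reduced model with group by time (6 parameters) and pattern by group (3) has full rank on the 9 observed cells. It gets there by assuming that drop-outs change as completers do. That is an identifying assumption, and the plan does not state it. The cited method could not be consulted; whatever it proposes, the three empty cells can be filled only by assumption.
- The 20% is described as a conservative allowance, and the side effects in Section 14 are described as mild or transient. Drop-out that differs by arm is possible, but the documents do not show it.

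**Conclusion.** The point holds in a limited form. The promise to establish whether drop-out is informative cannot be kept with observed data, and the pattern-mixture model lacks the assumption that would make its T2 means estimable. This is a stated procedure that cannot work as written, and more than missing detail. The consequence is that no analysis departing from missing at random is assured, while the first-listed comparison uses completers only.

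The size is moderate and rests on assumption: 0.10 to 0.20 SD for a departure of 0.5 to 1.0 SD confined to one arm at the full 20% loss. The figure of 27% of the planned effect is the upper end of that range and should not be read as an expected bias. The power figures of 40% and 18% follow from the plan's own numbers and an assumed baseline difference. They concern completely random drop-out only.

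The study is an exploratory pilot, which lowers the stakes. The change is still worth making, because the estimates are meant to feed a larger trial and the repair is cheap.

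**What to change.** Replace the missing-data sentences of the Analytic Approach with one paragraph that does the following.

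1. Drops the test of informativeness as a trigger. Any test of completely random drop-out is kept as descriptive only.
2. Names the mixed model using all T1 data, valid under missing at random, as the main analysis in place of the completer change-score t-tests.
3. Always reports a delta-adjusted (tipping-point) pattern-mixture analysis. It should be limited to scalar outcomes named in advance, because a shift has no clear direction for 16S community structure as a whole. The shift should vary separately in the synbiotic, *Triphala*-alone and placebo arms over a stated range, such as 0 to 1 SD in either direction. Shifting the synbiotic arm alone would not suit a trial in which two arms take *Triphala*. The report states the shift at which the conclusion changes.
4. Reports drop-out and exit-interview reasons by arm. The plan already records both; the breakdown by arm is new.

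Cost: a short SAP paragraph and a little extra analysis. No new data and no change to visits.

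### Continuous outcomes are adjusted for T1 only with the slope fixed at 1; prespecify T1 adjustment with an estimated slope, and name any other covariates in advance

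*Combined protocol and SAP*

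**What the plan says.** The only statistical text is Statistical Issues in Section 9. Its Analysis Plan paragraph lists three analyses.

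- Two-sample t-tests, "used to compare change scores (post-treatment minus pretreatment) in each outcome".
- O'Brien's test, whose "test statistic is a weighted linear combination of the" t-statistics for the separate outcomes.
- Mixed models with a subject-specific intercept: "Main covariate effects will be treatment group, time (pre-treatment and immediately post-treatment), and the group X time interaction".

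On covariates, the Analytic Approach paragraph compares the arms at baseline "using 2-sample tests to test if randomization achieved balance in key covariates across groups". It then says: "In the event of pre-existing variable group differences associated with dependent or relevant clinical variables, the nuisance variables will be statistically controlled". It gives no threshold, covariate list or model form.

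The Randomization paragraph says that allocation is meant "to ensure that participant demographics are evenly distributed across study conditions". It does not name those demographics, and no section places them in the analysis model. Under Assessment visits, the T1 measures are taken again at T2, so the baseline value of each repeated outcome will be in hand.

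**The concern.** A change score subtracts the whole T1 value, which fixes its coefficient at 1. If the true regression slope of T2 on T1 differs from 1, the change score carries avoidable noise. With only 20 completers per arm, and with results that Sample Size and Power says should inform a larger trial, interval width matters.

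The second problem is that the covariate set depends on the data. The plan records many variables in three arms, so some chance baseline differences are to be expected. Two analysts applying the rule could not be sure of fitting the same model.

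**Working it through.** **Inputs from the documents.** Section 10 gives 60 completers, 20 in each of three arms. Sample Size and Power gives two-sided alpha 0.05, d = 0.75 and 20% dropout. No T1-T2 correlation r and no SDs are given, so r and k = SD(T2)/SD(T1) are assumed and varied.

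**The plan's own figures.** 60/(1 − 0.20) = 75 recruited reproduces. The stated 80% power does not reproduce for 20 v 20 at d = 0.75: the exact t-test gives 63.7% (38 df), or 64.5% with the error variance pooled over three arms (57 df). That is a separate matter and decides nothing here.

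**Step 1: the mixed model is the change-score analysis.** T1 is a response with a free mean in each arm. With two complete visits, the interaction contrast is the difference in mean change. On simulated three-arm data with k = 1.25, both gave estimate 0.697534 and SE 0.337202. So the three analyses rest on the same use of T1.

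**Step 2: residual variances.** In units of the T1 variance:

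- change score: 1 + k² − 2rk
- T2 adjusted for T1 with an estimated slope: (1 − r²)k²
- difference: (1 − rk)², never negative, and zero only when rk = 1

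The variance ratio is V = (1 − r²)k² / (1 + k² − 2rk), which becomes (1 + r)/2 when k = 1.

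**Step 3: cost of estimating the slope.** With error df ν before adjustment and q added terms, chance imbalance multiplies the variance of the contrast on average by 1 + q/(ν − q − 1). The ratio of CI widths, adjusted over change score, is

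t(0.975, ν − q)/t(0.975, ν) × √{[1 + q/(ν − q − 1)] × V}.

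For T1 alone (q = 1) at V = 1:

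- three-arm model, ν = 57: (2.00324/2.00247) × √(1 + 1/55) = 1.0094
- pairwise 20 v 20, ν = 38: (2.02619/2.02439) × √(1 + 1/36) = 1.0147

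**Step 4: average change in CI width, three-arm model.** Example at k = 1, r = 0.5: √0.75 × 1.0094 = 0.874, so 12.6% narrower.

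| r | k = 1 | k = 1.25 | k = 0.8 |
|---|---|---|---|
| 0.3 | 18.6% narrower | 10.6% narrower | 28.5% narrower |
| 0.5 | 12.6% narrower | 4.6% narrower | 23.7% narrower |
| 0.7 | 6.9% narrower | 0.0% | 20.0% narrower |
| 0.8 | 4.2% narrower | 0.9% wider | 19.2% narrower |
| 0.9 | 1.6% narrower | 1.6% narrower | 21.3% narrower |

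Simulation (40,000 trials per setting) agreed at k = 1. Pairwise models at k = 1 gain slightly less: 18.2%, 12.1%, 6.4%, 3.7% and 1.1%.

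**Step 5: the downside is an average, not a ceiling.** With slope 1, the simulated 95th percentile of widening was 3.8% (three-arm) and 5.8% (pairwise).

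**Step 6: extra covariates unrelated to outcome.** At V = 1 in the three-arm model:

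- T1 plus two terms (q = 3): (2.00488/2.00247) × √(1 + 3/53) = 1.029
- T1 plus five terms (q = 6): (2.00758/2.00247) × √(1 + 6/50) = 1.061

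**Step 7: unequal arm variances.** Suppose the herb arm has 1.3 times the residual SD of the others. The pooled variance is (1 + 1 + 1.69)/3 = 1.23. For synbiotic v placebo the correct variance is 1, so the pooled CI is √1.23 = 1.11 times too wide. For synbiotic v herb it is (1 + 1.69)/2 = 1.345, so the CI is √(1.23/1.345) = 0.956 of its proper width. Simulated type I error was 0.032 and 0.063 respectively.

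**The case against.** **T1 is already used.** True. A reader might infer that the plan ignores baseline, or that its comparisons are biased. The documents support neither: change scores subtract T1, the mixed model carries it as a response, and both are valid under randomisation. Only the estimated slope is missing.

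**The gain rests on unknowns.** True. It is nil near rk = 1 and under 2% at k = 1, r = 0.9. The Psychological health list credits one life-satisfaction scale with high temporal reliability, so r may well be high there. The uncertainty limits the size of the claim, but the average cost of being wrong is small.

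**The cost may exceed 1%.** This stands. A reader might take 1% as an upper bound; it is an average for the three-arm model with T1 as the only covariate.

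**Pooling three arms assumes equal variances.** This stands, and the documents give reason for doubt. Background and Significance describes variable efficacy of herbal preparations and hypothesises that the probiotic makes response more uniform. The planned mixed model pools too, but the planned t-test does not pool in the third arm. The fix needs a safeguard.

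**The primary aim is barely touched.** Largely true. That aim concerns the stool microbiome, and sequencing is meant to "identify alterations in the gut microbiota community structure by 16S rDNA sequencing". This point reaches only scalar summaries that the team chooses to define.

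**The imbalance rule may not cover T1 outcome values.** Possibly; the text speaks of key covariates and nuisance variables. If so, there is no route to T1 adjustment with an estimated slope, which leaves the point intact.

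**Conclusion.** The point holds for continuous scalar outcomes, as a matter of precision and prespecification. No planned analysis adjusts for T1 with an estimated slope, and the choice of other covariates waits on the data.

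With 20 per arm and k = 1, the average narrowing of the 95% CI is about 19%, 13%, 7%, 4% and 2% across r = 0.3 to 0.9. It is larger at k = 0.8 and small to nil at k = 1.25. When rk = 1, the CI is on average about 1% wider (three-arm) or 1.5% wider (pairwise), and it exceeds about 4% to 6% wider in 5% of trials. With unrelated covariates added, the average becomes about 3% (two) and 6% (five). These figures assume normal outcomes, 20 completers per arm and equal residual variances across arms; r and k are assumptions throughout.

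A reader might also infer that T1 adjustment rescues the stated 80% power. It cannot be claimed to: the documents do not say on which SD scale d = 0.75 is defined, and they give no r.

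**What to change.** In the analysis plan, for each continuous scalar outcome (inflammatory markers, blood pressure, questionnaire scores, and any scalar microbiome summary named in advance):

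1. Name one primary model: a mixed model for T1 and T2 with T1 means constrained equal across the three arms and T1 and T2 variances free. It keeps participants who miss T2, which matters with 20% dropout allowed for. With complete data it is close to regressing T2 on arm and T1.
2. Report synbiotic v placebo and synbiotic v herb, each with a 95% CI.
3. State how unequal arm variances are handled: arm-specific residual variances, heteroscedasticity-robust standard errors with a small-sample correction, or pairwise T1-adjusted models. Choose one in advance.
4. Build O'Brien's test from the T1-adjusted t-statistics, taking the between-outcome correlation from the residuals of the adjusted models.
5. Replace covariate selection from baseline tests with at most a few covariates named in advance, for example those used in the allocation if they are few. Keep the baseline table descriptive.

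The cost is plan wording and one degree of freedom per outcome for T1, plus one for each further covariate term. No new data or visits are needed.
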